Study Document Cover Page

Official Title: : The Effects of Cardiovascular Autonomic Neuropathy (CAN) on Acute Kidney Injury and Outcome Parameters in Patients Undergoing Isolated Coronary Artery Bypass Grafting (CABG)

NCT Number:

NCT ID not yet assigned

Document Type:

Study Protocol with Statistical Analysis Plan and Informed Consent Form

Document Date:

October 1, 2020

Sponsor / Institution:

Akdeniz University Faculty of Medicine, Department of Anesthesiology and Reanimation

Principal Investigator:

[name]

Contact Information:

[contact]

Study Protocol

Title: The Effects of Cardiovascular Autonomic Neuropathy (CAN) on Acute Kidney Injury and Outcome Parameters in Patients Undergoing Isolated Coronary Artery Bypass Grafting (CABG)

Document Date: October 1, 2020

Institution: Akdeniz University Faculty of Medicine, Department of Anesthesiology and Reanimation

Principal Investigator: [name]

1. Study Objective

This study aims to analyze the effects of cardiovascular autonomic neuropathy (CAN) on primary outcome of acute kidney injury (AKI) and secondary outcome parameters in patients undergoing coronary artery bypass grafting (CABG) with extracorporeal circulation (ECC).

Specifically, the study will investigate:

The incidence of CAN in patients scheduled for isolated CABG

The effect of CAN on AKI

The impact of CAN on outcome parameters (mortality and morbidity)

The relationship between changes in regional cerebral oxygen saturation (rSO_2) and CAN

CAN Diagnosis:

1. Valsalva maneuver
2. Sitting-to-standing test
3. Temperature sensitivity test

2. Materials and Methods

This is a prospective multicenter study including all patients scheduled for CABG requiring ECC.

Preoperative CAN diagnosis will be performed 1 day before surgery using Valsalva maneuver, sitting-to-standing test, and temperature sensitivity test. A positive result in at least two tests will confirm CAN.

Preoperative data to be recorded:

Demographics and comorbidities (hypertension, diabetes, COPD, recent MI, atrial fibrillation, dyslipidemia)

Kidney function (BUN, creatinine, GFR)

Hemodynamic parameters before anesthesia induction

Baseline rSO_2 (monitoring will be blinded for clinical purposes)

Intraoperative data:

Hemodynamics, urine output, blood gases

Total cardiopulmonary bypass time, aortic cross-clamp time

Number of coronary artery anastomoses

Postoperative data:

rSO₂ at 1st and 4th hours, and 60 minutes after extubation

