Statistical Analysis Categorical variables will be presented as counts and percentages. Between-group comparisons for categorical variables will be performed using the chi-square test. The distribution of continuous variables will be evaluated using skewness and kurtosis. Variables with distribution between -1.5 and +1.5 will be considered normally distributed (parametric), otherwise non-parametric. Parametric continuous variables will be expressed as mean \pm SD. Between-group comparisons will be performed using the independent Student's t-test, and within-group temporal comparisons using the paired Student's t-test. Non-parametric continuous variables will be presented as median and interquartile range (IQR). Between-group comparisons for non-parametric variables will be performed using the Mann-Whitney U test, and within-group temporal comparisons using the Wilcoxon signed-rank test. Correlation analysis will be conducted using Pearson (parametric) or Spearman (non-parametric) correlation coefficients. Factors affecting AKI and neurological complications will be evaluated using multiple regression analysis.

Sample Size Calculation The primary objective of this study is to compare the incidence of AKI between CAN-positive and CAN-negative patients undergoing coronary artery bypass grafting (CABG). Based on previous studies using heart rate variability (HRV) for CAN diagnosis, the prevalence of CAN after myocardial infarction (MI) is approximately 60%. In the CABG population, approximately 30% of patients have diabetes and/or MI. Therefore, we anticipate a CAN prevalence of at least 20%. Postoperative AKI incidence ranges from 12–36% in the literature. Assuming that at least 20% of our patients will be CAN-positive and that AKI incidence in CAN-positive patients will be at least 10% higher than in CAN-negative patients, with $\alpha = 0.05$ and $\beta = 0.2$, a minimum of 884 patients will be required.

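### The primary AKI comparison is unadjusted although the plan's own prevalence reasoning puts diabetes/MI mostly in CAN-positive patients, and beta 0.2 covers only that unadjusted comparison

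*Combined protocol and SAP*

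**What the plan says.** Section 1 (Study Objective) lists among its aims "The effect of CAN on AKI". The Sample Size Calculation words the primary objective as a comparison of AKI incidence between CAN-positive and CAN-negative patients.

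For the analysis, the Statistical Analysis section says: "Between-group comparisons for categorical variables will be performed using the chi-square test". The only route to adjustment is one sentence: "Factors affecting AKI and neurological complications will be evaluated using multiple regression analysis". It names no model type and no covariates, does not say that CAN is in the model, and is not linked to the primary objective.

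The prevalence reasoning has three steps:
- From earlier HRV-based studies, "the prevalence of CAN after myocardial infarction (MI) is approximately 60" per cent.
- "In the CABG population, approximately 30% of patients have diabetes and/or MI".
- "Therefore, we anticipate a CAN prevalence of at least 20" per cent.

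The effect is that "AKI incidence in CAN-positive patients will be at least 10% higher than in CAN-negative patients". With alpha 0.05 and beta 0.2, this gives a minimum of 884 patients. The CAN-negative AKI rate is not stated (only a literature range of 12–36% for AKI), nor is the sidedness. Section 2 (Materials and Methods) records "Demographics and comorbidities (hypertension, diabetes, COPD, recent MI, atrial fibrillation, dyslipidemia", along with kidney function including GFR.

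**The concern.** The prevalence argument works only because CAN is concentrated in patients with diabetes/MI. The plan therefore predicts that the two groups will differ sharply in diabetes/MI, and then compares them with a test that ignores the difference. If diabetes/MI affects AKI at all, a significant chi-square result cannot be attributed to CAN.

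A regression could separate the two, but the stronger CAN's association with diabetes/MI, the less information is left on CAN itself. The 884 makes no allowance for this. At stake are a positive result that cannot be interpreted, or a null adjusted result that a reader takes to have 80% power behind it.

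**Working it through.** **Reproducing 884.** Inputs: CAN-positive 20%, CAN-negative 80% (1:4), alpha 0.05, power 0.80. I assume AKI of 20% v 30%, two-sided, no continuity correction. Pooled rate = 0.2×0.30 + 0.8×0.20 = 0.22.

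n(CAN-positive) = [1.96×√(0.22×0.78×1.25) + 0.8416×√(0.30×0.70 + 0.20×0.80/4)]² / 0.10² = (0.9077 + 0.4208)² / 0.01 = 176.5.

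The total is 5×176.5 = 882.5. Rounding each group up gives 177 + 707 = 884, and power at 884 is 80.1%. The stated number is reproduced.

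**Imbalance implied by 60%, 30% and 20%.** Per 100 patients, 30 have diabetes/MI, and 0.60×30 = 18 of these are CAN-positive. With 20 CAN-positive in all, 2 of the other 70 (2.9%) have CAN. Diabetes/MI is then present in 18/20 = 90% of CAN-positive and 12/80 = 15% of CAN-negative patients.

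**Chi-square test when CAN has no effect.** If diabetes/MI shifts AKI by d points, the crude CAN difference is (0.90 − 0.15)×d = 0.75d. With overall AKI 22%, SE = √[0.22×0.78×(1/176.8 + 1/707.2)] = 3.48 points.
- d = 5: difference 3.75, z = 1.08, rejection about 19% (simulated 19.7%).
- d = 10: difference 7.5, z = 2.15, rejection about 58% (simulated 57.1%).

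If CAN is 40% in the diabetes/MI group and 20% overall, the shares are 60% v 22.5% and the crude difference is 0.375d. Simulated rejection is then 8.9% (d = 5) and 19.7% (d = 10). The values of d are my assumptions.

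**Power adjusted for diabetes/MI at N = 884.** I use logistic regression of AKI on CAN and diabetes/MI, with 20% v 30% AKI and no diabetes/MI effect. The log odds ratio is ln[(0.30/0.70)/(0.20/0.80)] = 0.539. The information is the sum over diabetes/MI strata of AB/(A+B), where A = 884 × P(CAN-positive, stratum) × 0.21 and B = 884 × P(CAN-negative, stratum) × 0.16.
- With diabetes/MI: A = 884×0.18×0.21 = 33.42, B = 884×0.12×0.16 = 16.97, giving 11.26.
- Without: A = 884×0.02×0.21 = 3.71, B = 884×0.68×0.16 = 96.18, giving 3.57.
- Sum 14.83, SE = 1/√14.83 = 0.260, z = 2.08, power = Φ(2.08 − 1.96) = 54.6% (simulated 54.5–54.8%).

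The same calculation for other prevalences, where c is overall CAN, q is CAN in diabetes/MI, and the diabetes/MI shares are 0.30q/c and 0.30(1−q)/(1−c):

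| CAN in diabetes/MI | CAN in the rest | CAN overall | Diabetes/MI share, CAN+ v CAN− | Adjusted power |
|---|---|---|---|---|
| 60% | 2.9% | 20% | 90% v 15% | 55% |
| 50% | 7.1% | 20% | 75% v 19% | 68% |
| 40% | 11.4% | 20% | 60% v 22.5% | 76% (simulated 75%) |
| 60% | 10% | 25% | 72% v 16% | 73% (simulated 72%) |
| 60% | 15% | 28.5% | 63% v 17% | 80% |
| 60% | 20% | 32% | 56% v 18% | 85% |
| 40% | 20% | 26% | 46% v 24% | 86% |

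**Dependence on the AKI rate, at 20% CAN.** For 12% v 22%, power is 90% unadjusted, and adjusted 67% (60% row) or 88% (40% row). For 36% v 46%, it is 68% unadjusted, and adjusted 45% or 63%.

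**The case against.** The strongest reply is that beta 0.2 belongs to the comparison that the plan names, which is incidence in two groups, and 884 delivers it. The plan makes no power claim for the regression. That stands. A reader might infer that 884 is miscalculated, or that the plan promises 80% power for an adjusted effect; the documents support neither.

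Second, 20% is stated as a minimum. The 90% v 15% split arises only at exactly 20% CAN, and the 60% is a post-MI, HRV-based figure applied to a wider group, while this study diagnoses CAN by at least two of three bedside tests. That also stands: the split is what the planning figures imply at their floor, not a forecast. A reader might take 55–75% as bounds on adjusted power. They are not: with 60%/15%, 60%/20% or 40%/20% CAN in the two groups, 884 already gives 80–86%, and no stated input is broken.

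Third, a reader might infer that recruitment should rise to 884/(1 − R²), where R² is the squared correlation between CAN and diabetes/MI. That ignores the CAN prevalence actually observed. With 60%/15%, R² is about 0.21 and the rule asks for about 1,117 patients where 884 gives 80%. The documents do not support a larger N on this ground.

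Fourth, the false-positive rates rest on assumed diabetes/MI effects. True, and they shrink as the imbalance shrinks. But the imbalance vanishes only if CAN is equally common with and without diabetes/MI, contrary to the plan's own reasoning.

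**Conclusion.** The point holds as a gap between the aim and the analysis. An effect of CAN on AKI is sought in non-randomised groups that the plan expects to differ in diabetes/MI. The named test does not adjust, and the regression that might is unspecified and not tied to the primary objective. The sample size is sound for what it covers, but its beta does not transfer to the adjusted effect when CAN is at the planned 20%.

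The conclusion rests on the inferred 20% v 30% AKI rates and a two-sided test. The adjusted-power figures also assume that the full 10-point CAN effect remains after adjustment and that diabetes/MI has no effect on AKI. If instead the 20% v 30% odds ratio holds within strata and diabetes/MI has an odds ratio of 1 to 2, adjusted power on the 60%/30%/20% inputs is about 55–62%. If only the crude difference is 10 points and diabetes/MI has an assumed odds ratio of 1.5, it falls to about 16%. The direction is firm; the size depends on CAN prevalence in each group and on the AKI rate, neither of which is yet known.

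**What to change.** 1. Name one primary analysis: logistic regression of AKI (yes/no) on CAN, adjusted for diabetes, MI and other prespecified baseline covariates already recorded (for example age, hypertension, baseline GFR). Report the unadjusted chi-square comparison beside it as descriptive.
2. Keep 884. State that beta 0.2 applies to the unadjusted comparison, and print the assumptions behind it: CAN-negative AKI rate, sidedness, and that the 10% is in percentage points. 20% and two-sided reproduce the figure; the sponsor should confirm them.
3. Give adjusted power as a table over CAN prevalence in each group and over the CAN-negative AKI rate. At 20% v 30%, the scenarios above run from about 55% to 86%.
4. Do not add a rule that rescales 884 by 1/(1 − R²).

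The cost is mainly text and no extra patients. One data field may be needed, because Section 2 records recent MI, which may not cover all previous MI. The downside is that the stated power for the adjusted effect will look less favourable than 80% over part of the range.
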